6.5.7 Statistical/Analytical Issues

6.5.7.1 Adjustment for Covariates

No adjustment for covariates will be performed.

6.5.7.2 Handling of Dropouts or Missing Data

The MI methods are as described in Section 6.5.6.2. In addition, analyses based on complete case, best case, worst-case, and complete case without COVID-19 population scenarios for the primary effectiveness endpoints will be performed.

6.5.7.3 Interim Analyses and Data Monitoring

No interim analyses or data monitoring committees are planned during this study. Members of the Sponsor team will review clinical data during the study conduct.

6.5.7.4 Multicenter Studies

This is a multicenter, prospective, open label, non-randomized, single arm study evaluating the safety and effectiveness of the Technolas TENEO 317 Model 2 (Version 1.28 US software) Excimer Laser when used in LASIK surgery to treat myopia or myopic astigmatism. Both eyes of a subject may be enrolled so long as both eyes meet all inclusion/exclusion requirements.

Any extreme or opposite results among centers will be examined.

6.5.7.5 Multiple Comparisons/Multiplicity

All primary effectiveness endpoints must be successful to demonstrate statistical success. Consequently, no adjustment is required for the primary effectiveness endpoints.

6.5.7.6 Use of an "Effectiveness Subset" of Subjects

This section is not applicable to the current analysis.

6.5.7.7 Active-Control Studies to Show Equivalence

This section is not applicable to the current analysis.

6.5.7.8 Examination of Subgroups

This section is not applicable to the current analysis.

6.5.8 Safety Analyses

The following safety summaries will be provided with descriptive statistics by visit for all treated eyes, eyes treated for spherical myopia, and eyes treated for astigmatic myopia unless otherwise specified.

- Eyes with BSCVA worse than 20/40 among eyes that had a BSCVA of 20/20 or better before surgery at each postoperative study visit, stratified by preoperative MRSE in 1.00-D unit ranges from -1.00 D to -12.00 D; by severity of preoperative myopia with > -7 D and <= -7 D; and by preoperative cylinder for ranges of 0, -0.25 to -0.50 D, -0.51 to -1.00 D, -1.01 D to -2.00 D, and -2.01 D to -3.00 D
- Loss of BSCVA of 1, 2, ≥ 2, and > 2 lines compared to preoperative BSCVA, with 95% CIs around the proportions
- Percentage of eyes that have an increase of manifest refractive astigmatism > 2.00
 D compared to the preoperative refraction (since all cylinder values will be converted to minus notation first, this is equivalent to change from baseline in cylinder <= -2 D), stratified by preoperative MRSE, and severity of preoperative myopia. A 95% CI around the percentage of all eyes that have an increase of > 2.00
 D will be displayed.
- Incidence of AEs by event type
- Incidence of complications
- Endothelial cell density changes
- Contrast sensitivity changes, mesopic conditions
- Subject symptoms and results for prespecified question domains (from Patient Reported Outcome with LASIK - Preoperative Questionnaire [PROWL-PRQ] [3] and Patient Reported Outcome with LASIK - Postoperative Questionnaire [PROWL-POQ] [4])

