9.6.3.3 Additional Safety Analyses

The following additional safety summaries will be provided with descriptive statistics by visit.

- Eyes with BSCVA worse than 20/40 among eyes that had a BSCVA of 20/20 or better before surgery at each study visit, stratified by preoperative MRSE, and stratified by preoperative cylinder
- Loss of BSCVA of 1, $2, \ge 2$, and > 2 lines
- Percentage of eyes that have an increase of manifest refractive astigmatism > 2.00 D of manifest cylinder compared to the preoperative refraction
- Eyes treated for sphere only that have a magnitude of postoperative manifest refractive astigmatism that increases from baseline cylinder by > 2.00 D at the postoperative interval at which stability has been established, and stratified by preoperative MRSE

- Incidence of adverse events by event type
- Frequency of miscreated flaps
- Incidence of complications
- Endothelial cell density changes
- Contrast sensitivity changes, mesopic conditions
- Schirmer's Test results, Preoperative Visit and Month 6 Visit
- Intraocular Pressure
- Subject symptoms and results for prespecified question domains (from PROWL questionnaire)

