6.5.8.3 Adverse Events and Unanticipated Adverse Device Effects

An AE is defined as any untoward medical occurrence, unintended disease or injury, or untoward clinical signs (including abnormal laboratory finds) in subjects, users, or other persons, whether or not related to the investigational medical device.

The following AEs are the key safety events surveilled during the study in order to assess conformity to the target values of "Incidence of Adverse Events".

- Loss of > 2 lines (10 letters) BSCVA
- BSCVA worse than 20/40
- BSCVA worse than 20/25 if 20/20 or better preoperatively
- Haze \geq trace with loss of BSCVA > 2 lines (10 letters)
- Increased manifest refractive astigmatism > 2.0 D
- Corneal epithelial defect involving the keratectomy at one month or later
- Melting of the flap
- Miscreated flap (lost, incomplete, too thin)
- Diffuse lamellar keratitis (Grade 3 or above)
- Corneal infiltrate or ulcer

- Any persistent corneal epithelial defect at one month or later
- Epithelium in the interface with loss of 2 lines (10 letters) or more BSCVA
- IOP with increase of > 10 mmHg above baseline on two consecutive examinations or an IOP greater than 30 mmHg on two consecutive examinations
- Haze beyond 6 months with loss of 2 lines or greater (≥ 10 letters ETDRS) of BSCVA
- Decrease in BSCVA of greater than or equal to 2 lines (≥ 10 letters ETDRS) not due to irregular astigmatism as shown by rigid contact lens refraction at 3 months or later
- Retinal detachment
- Corneal edema at 1 month or later
- Retinal vascular accidents
- Ocular penetration
- Other ocular event

All UADEs are considered to be rare, unanticipated events and have a serious effect on health or safety or represent any life-threatening problem or death caused by the device, if the event has not previously been identified in the investigational plan. A UADE may include, but is not limited to, the following events:

- Device-related death
- Enucleation of treated eye
- Corneal transplant of treated eye

A summary (counts and percentages) of AEs/UADEs will be presented by incidence of AEs for operative visit, each postoperative study visit, and overall (a Total column) using all treated eyes. At a study visit subjects' eyes will be counted only once if they experience multiple AEs/UADEs of the same type and similarly will be counted only once in Total column if they have AEs/UADEs of the same type at multiple study visits.

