- 95% CIs for percentage of eyes with the loss of BSCVA of 1, 2, ≥ 2, and > 2 lines compared to preoperative BSCVA and for percentage of eyes that have an increase of manifest refractive astigmatism > 2.00 D compared to the preoperative refraction will be presented.
- The percentage of eyes with at least one serious, device-related adverse event during the study along with 95% CI will be presented.
- Contrast sensitivity results will not be reported as graphs as stated in the protocol but will be summarized in a table.
- Schirmer's test results will not be summarized in a table.
- Intraocular pressure results will not be summarized in a table.
- Changes to questionnaire data analysis.
 - In the protocol, Table 3 has questions for topics Visual Functions and Near Vision overlapped. In SAP, topic Vision Functions is removed, and questions are combined under Near Vision.
 - Topic Expectation of LASIK Surgery in protocol Table 4 is considered a subjective measure that may have potential threats to the validity. The results will not be summarized but only provided in questionnaire listing.
 - Questions not covered in protocol Table 3 and Table 4 are not the main interest to the study. The results will not be summarized but only provided in questionnaire listing.

Documentation of revision to the SAP will commence after approval of Version 1.0.

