7 REFERENCES

1. ANSI Z80.11-2012 (R2017) standard - Laser Systems for Corneal Reshaping

3. LASIK Pre-Operative Questionnaire (PRQ). (2015, June 4). Retrieved from https://www.fda.gov/downloads/MedicalDevices/ProductsandMedicalProcedures/Surgerya ndLifeSupport/LASIK/UCM528837.pdf

4. LASIK Post-Operative Questionnaire (POQ). (2015, June 2). Retrieved from https://www.fda.gov/downloads/MedicalDevices/ProductsandMedicalProcedures/Surgerya ndLifeSupport/LASIK/UCM528841.pdf

6. Engineering Report ER-100022264: Data analysis report of patients with preoperative only spherical myopia or myopic astigmatism, Technolas Document #100022264.

8 APPENDIX 1

Vector analyses

The following pre-analysis transformations will be done:

- 1. Convert manifest refraction to positive cylinder notation.
- 2. Convert all manifest refraction data from the spectacle to the corneal plane (adjusting for vertex distance) using the following formula:

$$MRC = \frac{1000 (Sph + Cyl)}{1000 - 13 (Sph + Cyl)} - \frac{1000 Sph}{1000 - 13 Sph}$$

Where

MRC = Refractive cylinder at the corneal plane Sph = Manifest refractive sphere

- Cyl = Manifest refractive cylinder
- 3. Adjust left eye axis as follows:

Adjusted Axis = $180^{\circ} - Original$ axis

Vector Analysis Variables:

- 1. The intended refractive correction vector (IRC) is defined as the vector difference between the preoperative astigmatic correction vector and the target postoperative cylinder vector (preoperative - target). If the target refractive state is emmetropia, the IRC vector is equal to the preoperative cylinder (i.e., MRC) and angle.
- 2. Surgically induced refractive correction (SIRC) vector is the vector difference between the preoperative and postoperative astigmatic correction vectors (preoperative postoperative).

Methods for calculating the refractive error analysis variables (from here onwards, C = MRC and A for left eye is the adjusted axis):

1. Convert the preoperative astigmatic correction to X and Y vector components:

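### The SAP's induced-astigmatism safety row is insensitive in eyes treated for moderate or high cylinder, and read literally its only confidence interval is on all eyes, not on the sphere-only eyes that the protocol singles out

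*SAP*

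**What the plan says.** SAP 6.5.8 lists a row described as "Percentage of eyes that have an increase of manifest refractive astigmatism > 2.00" D compared with the preoperative refraction. It translates this for programming, in minus-cylinder notation, as "this is equivalent to change from baseline in cylinder <= -2 D". The row is stratified by preoperative MRSE and by severity of myopia, but not by preoperative cylinder. The interval is described as "A 95% CI around the percentage of all eyes that have an increase of > 2.00" D.

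The opening sentence of 6.5.8 gives the safety summaries by visit "for all treated eyes, eyes treated for spherical myopia, and eyes treated for astigmatic myopia unless otherwise specified". SAP 6.6 restates the interval as one for the "percentage of eyes that have an increase of manifest refractive astigmatism > 2.00 D compared to the preoperative refraction will be presented", without confining it to the pooled set. SAP 6.5.6.1 makes intervals for single proportions two-sided at 95%, and no method is given for this row.

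Protocol 9.6.3.3 has two bullets on the subject. The first is the general percentage. The second is specific: "Eyes treated for sphere only that have a magnitude of postoperative manifest refractive astigmatism that increases from baseline cylinder by > 2.00 D", at the interval where stability is established and stratified by preoperative MRSE. SAP 6.5.8 has no separate bullet for the second, and SAP 6.6 does not list it as dropped. The adverse event list in SAP 6.5.8.3 carries the related category "Increased manifest refractive astigmatism > 2.0 D", tabulated on all treated eyes.

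**The concern.** An increase over baseline means different things in different eyes. In an eye with no cylinder before surgery, it is the astigmatism that the procedure added. In an eye treated for cylinder C, the procedure is meant to remove C, and that removal is credited against anything added or misplaced. One threshold of 2.00 D thus sets a different test in each cylinder bin, and the row is not stratified by the variable that moves the test.

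The interval adds to this. If it is given only for all treated eyes, the group in which the measure works contributes perhaps a tenth of the denominator. The rest is largely eyes that have to clear a higher bar. A short interval near zero could then be read as a tight bound on induced astigmatism, which it would not be.

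**Working it through.** **Inputs.** Sample size: 300 evaluable eyes from 334 treated, allowing 10% loss (SAP 6.5.9.5). Cylinder bins: at least 30 eyes in each of five, including the zero-cylinder column (SAP Table 1). Treated cylinder: 0 to 3.00 D in magnitude (SAP 6.2.1). Refraction: 0.25 D steps (Protocol Appendix B, 7.0). The documents give no expected rate for this event, so the event counts below are assumptions.

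**The plan's own figure.** 300 / (1 − 0.10) = 333.3, rounded up to 334, as stated. The induced-astigmatism row has no target or power of its own to reproduce.

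**Step 1: the bar by preoperative cylinder.** An eye counts under the stated wording if postoperative cylinder > C + 2.00 D.

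| Preoperative C (D) | Postoperative cylinder must exceed (D) |
|---|---|
| 0 | 2.00 |
| 0.25 | 2.25 |
| 0.50 | 2.50 |
| 1.00 | 3.00 |
| 2.00 | 4.00 |
| 3.00 | 5.00 |

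**Step 2: misdirected correction.** Suppose a full correction is placed θ degrees off axis. In double-angle vectors the residual is 2C sin θ, so the recorded increase is C(2 sin θ − 1).
- Increase > 2.00 D requires sin θ > (C + 2)/(2C). At C = 3.00 this is 5/6, or θ > 56.4°. At C = 2.50 it is 0.90, or θ > 64.2°. At C = 2.00 it is 1, so the increase reaches 2.00 D only at 90° and never exceeds it. Below 2.00 D there is no solution.
- Residual > 2.00 D requires sin θ > 1/C, which is θ > 19.5° at C = 3.00 and θ > 23.6° at C = 2.50.

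**Step 3: pure over-correction.** If C = 3.00 D is corrected twice over on axis, 3.00 D remains at the opposite axis and the recorded increase is 3.00 − 3.00 = 0.

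**Step 4: the interval.** Assume all x events fall in n sphere-only eyes. The pooled percentage is then lower by the factor 300/n. Clopper-Pearson 95% intervals:

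| Events | 30 sphere-only eyes | All 300 eyes |
|---|---|---|
| 0 | 0% (0 to 11.6%) | 0% (0 to 1.2%) |
| 1 | 3.3% (0.1 to 17.2%) | 0.33% (0.01 to 1.8%) |
| 3 | 10.0% (2.1 to 26.5%) | 1.0% (0.2 to 2.9%) |

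The factor is 10 at n = 30, 5 at n = 60, 3 at n = 100 and 1.67 at n = 180. The last is the most possible if the other four cylinder bins hold 30 each (300 − 4 × 30 = 180).

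**Step 5: the inequality.** For changes of −1.75, −2.00 and −2.25 D, the stated wording counts only the third, while the coded rule counts the second and third. With 0.25 D steps a change of exactly −2.00 D can occur, so the two are not equivalent.

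**The case against.** The strongest reply is that the row does what it says. It implements the protocol's general bullet, and the opening sentence of 6.5.8 gives eyes treated for spherical myopia their own table at every visit, including the stability visit. That stands. A reader might infer that the sphere-only *rate* is diluted; it is not, and only the interval is in question.

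Even the interval is arguable. *All eyes* may mean the overall line of each table, as against its MRSE strata, and SAP 6.6 does not limit it. Against that, Protocol 9.6.3.1 uses the term for the pooled set beside the spherical and astigmatic sets, and the preceding SAP bullet, on loss of BSCVA, asks for intervals without that limit. The text supports both readings.

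A reader might also infer that eyes treated for astigmatism can hardly ever be counted. The documents give no event rate to support that, and eyes at −0.25 to −0.50 D need only 0.25 to 0.50 D more postoperative cylinder than sphere-only eyes.

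Nor do axis and cylinder errors go unseen in the plan as a whole. SAP 6.5.6.3.1 tabulates residual astigmatic error against axis shift, and the correction ratio. SAP 6.5.6.5.1 gives axis shift, error of angle beyond 15 degrees, and cylinder within 2.00 D of intended. The 19.5° and 23.6° cases above would both fall in the beyond-15-degree categories.

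A further temptation is to use Appendix 1, where "Surgically induced refractive correction (SIRC) vector is the vector difference between the preoperative and postoperative astigmatic correction vectors", and count eyes with |IRC − SIRC| > 2.00 D as induced astigmatism. With an emmetropic target, which SAP 6.5.4.2 states for all eyes, that difference is simply the postoperative cylinder vector. It would count under-correction as induced and, apart from the vertex conversion, largely repeat the complement of the existing row for cylinder within 2.00 D of intended.

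Finally, the raised cylinder conversion factor (Protocol 5.1) changes magnitude, not axis, so it is no ground for expecting the axis errors in Step 2.

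**Conclusion.** The concern holds in a limited form. The row measures induced astigmatism in sphere-only eyes, is little affected at −0.25 to −0.50 D, and is insensitive from about 1 D of treated cylinder upwards. Read literally, its one named interval is on the pooled set, where the percentage is lower by a factor of 1.67 to 10. With no events at the planned minimum of 30 sphere-only eyes, the data would exclude rates above 11.6% in that group, not above 1.2%.

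These figures assume that all events are in sphere-only eyes, that eyes treated for spherical myopia are those in the zero-cylinder column, that 300 eyes are evaluable, and that eyes are independent, as SAP 6.5.6.1 specifies. Step 2 also assumes a full correction with axis error alone. The mismatch between the stated and coded thresholds needs none of these assumptions. No primary endpoint is affected.

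**What to change.** In SAP 6.5.8:

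1. State that an exact two-sided 95% CI is given for eyes treated for spherical myopia at the stability visit, the item in Protocol 9.6.3.3, as well as for all treated eyes. Naming the method matters because a normal-approximation interval has zero width at 0 events. Add that the all-eyes interval is not to be read as the induced-astigmatism rate.
2. For eyes treated for astigmatism, show beside it the proportion with cylinder more than 2.00 D from intended, which is the complement of the existing row in SAP 6.5.6.5.1, with a 95% CI. Label it residual cylinder error, not induced astigmatism.
3. Make the stated threshold and the coded rule agree on whether a change of exactly 2.00 D counts.

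The cost is a few sentences in the SAP and a few lines of code, with no new data. The downside is a wider and less favourable interval for sphere-only eyes.

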6.5.8.1 Extent of Exposure

This section is not applicable to this device study.

6.5.8.2 Adverse Safety Events

Each eye treated must be examined for the presence or absence of adverse safety events at all visits, whether scheduled or not. The collection of safety events begins at the time the subject signs the ICF. For the purposes of this study, adverse safety events are defined broadly to include a range of events encompassing four hierarchical categories of risk: AEs, UADEs, complications/potential AEs, and symptoms. Adverse events represent the key safety events that are surveilled during the study. Unanticipated adverse device events represent rare, unanticipated safety events directly attributable to the device. Other safety events include anticipated complications/potential AEs known to occur following laser refractive surgery and subjective symptoms reported by the subjects.

All AEs, UADEs, and complications/potential AEs will be presented by the AE categories in the eCRF. The data listings by subject will present the categories of AE in the eCRF along with their coded AE term using MedDRA, Version 22.0.

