8.1 Adverse Events

An adverse event (AE) as defined in ISO standard 14155 is "any untoward medical occurrence, unintended disease or injury, or untoward clinical signs (including abnormal laboratory findings) in subjects, users, or other persons, whether or not related to the investigational medical device."

The following AEs are the key safety events surveilled during the study. Each occurrence of these AEs must be reported to the Sponsor by recording in the AE CRF within 48 hours, and in addition, must be reported to the IRB per IRB policy (See Table 2).

- Loss of > 2 lines (10 letters) BSCVA
- BSCVA worse than 20/40
- BSCVA worse than 20/25 if 20/20 or better preoperatively
- Haze \geq trace with loss of BSCVA > 2 lines (10 letters)
- Increased manifest refractive astigmatism > 2.0 D
- Corneal epithelial defect involving the keratectomy at one month or later
- Melting of the flap
- Miscreated flap (lost, incomplete, too thin)
- Diffuse lamellar keratitis (Grade 3 or above) ⁴²
- Corneal infiltrate or ulcer
- Any persistent corneal epithelial defect at one month or later
- Epithelium in the interface with loss of 2 lines (10 letters) or more best spectacle corrected visual acuity (BSCVA)
- Intraocular Pressure (IOP) with increase of >10 mmHg above baseline on two consecutive examinations or an IOP greater than 30 mmHg on two consecutive examinations
- Haze beyond 6 months with loss of 2 lines or greater (≥ 10 letters ETDRS) of BSCVA
- Decrease in BSCVA of greater than or equal to 2 lines (≥ 10 letters ETDRS) not due to irregular astigmatism as shown by rigid contact lens refraction at 3 months or later
- Retinal detachment
- Corneal Edema at 1 month or later
- Retinal vascular accidents
- Any other vision-threatening event
- Ocular penetration

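### AE incidence rests on site-entered categories, although 11 of the 20 listed AEs are thresholds on recorded measurements; no programmed derivation or reconciliation is specified, and three of the 11 have no measurement-based table

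*SAP*

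**What the plan says.** On the source of the AE table, SAP 6.5.8.2 states: "All AEs, UADEs, and complications/potential AEs will be presented by the AE categories in the eCRF". The listings pair those categories with a MedDRA term. On who makes the entry, Protocol 8.1 states: "Each occurrence of these AEs must be reported to the Sponsor by recording in the AE CRF within 48 hours". Table 2 in Protocol section 8 repeats this.

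On purpose, SAP 6.5.8.3 states: "The following AEs are the key safety events surveilled during the study in order to assess conformity to the target values". It names AE incidence as the quantity concerned but gives no target values.

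The list that follows has 20 entries. Many are rules on measurements, for example "Loss of > 2 lines (10 letters) BSCVA", "Increased manifest refractive astigmatism > 2.0 D" and "IOP with increase of > 10 mmHg above baseline on two consecutive examinations".

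Separately, SAP 6.5.8 plans by-visit tables taken from measurements. One is "Loss of BSCVA of 1, 2, ≥ 2, and > 2 lines compared to preoperative BSCVA", with 95% confidence intervals. Another is the percentage of eyes with an astigmatism increase above 2.00 D. A third is BSCVA worse than 20/40 among eyes that were 20/20 or better before surgery. IOP (SAP 6.5.8.8) and slit-lamp findings (SAP 6.5.8.12) are listed by subject and not summarized.

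**The concern.** Whether a measured value crosses a fixed limit is a calculation, not a clinical judgement. Several of these limits need a comparison with the preoperative value, and the IOP limit needs two examinations in a row. If the AE table takes these rows only from what a site entered, an overlooked crossing drops out of the table even though the values that prove it are in the database.

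Protocol 8.4 makes misfiling plausible. Several threshold AEs have a milder neighbour in the complications list: haze, epithelium in the interface, DLK grade 2 or less, and edema before 1 month. Those are recorded only on the postoperative forms.

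The study is open-label and single-arm, and SAP 6.5.7.3 plans no data monitoring committee. Omitted entries can only lower the incidence that the SAP intends to compare with target values. Where a measurement-based table does exist, it may disagree with the AE table, and nothing says which of the two is the source for that comparison.

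**Working it through.** **1. Count.** Going through the 20 entries of SAP 6.5.8.3 in order, 11 are thresholds on recorded measurements. The other nine are clinical findings without such a limit (for example flap melting, corneal infiltrate or ulcer, retinal detachment).

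| Entry | Rests on | Measurement-based table in SAP 6.5.8 |
|---|---|---|
| 1 BSCVA loss > 2 lines | BSCVA | Line-loss table |
| 2 BSCVA worse than 20/40 | BSCVA | Own table for a subset of eyes; also line-loss table |
| 3 Worse than 20/25 if 20/20 or better before | BSCVA | Line-loss table |
| 4 Haze with loss > 2 lines | Slit lamp, BSCVA | Line-loss table (BSCVA part) |
| 5 Astigmatism increase > 2.0 D | Refraction | Own table |
| 9 DLK grade 3 or above | Slit lamp | None |
| 12 Interface epithelium with loss of 2 lines or more | Slit lamp, BSCVA | Line-loss table (BSCVA part) |
| 13 IOP | IOP | None |
| 14 Haze after 6 months with loss of 2 lines or more | Slit lamp, BSCVA | Line-loss table (BSCVA part) |
| 15 Loss of 2 lines or more, with rigid-lens condition | BSCVA, rigid-lens result | Line-loss table (BSCVA part) |
| 17 Corneal edema from 1 month on | Slit lamp | None |

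**2. Why the line-loss table reaches entries 2 and 3.** SAP 6.5.6.2 gives logMAR = 1.7 − 0.02 × letters, rounded to one decimal. It is stated for UCDVA; I assume it also holds for BSCVA.

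- Entry 2: eligibility requires 20/25 or better, so at least 78 letters (1.7 − 1.56 = 0.14, rounds to 0.1). Worse than 20/40 means at most 67 letters (1.7 − 1.34 = 0.36, rounds to 0.4). The loss is at least 78 − 67 = 11 letters. Without rounding it is 80 − 69 = 11.
- Entry 3: 20/20 or better needs at least 83 letters (0.04, rounds to 0.0). Worse than 20/25 means at most 77 (0.16, rounds to 0.2). The loss is at least 83 − 77 = 6 letters. Without rounding it is 85 − 79 = 6.

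SAP 6.5.6.5.1 takes lines as the integer part of letters / 5. If this also applies in 6.5.8, 11 letters gives 2 lines and 6 letters gives 1 line. Entries 1, 4, 12, 14 and 15 require at least 10 letters, hence at least 2 lines. At visits that the by-visit tables cover, the vision loss behind all seven BSCVA-based entries is therefore tabulated. With entry 5 that makes 8 of 11. The remaining three are 9, 13 and 17.

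**3. Where the definitions part.**

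- Entry 1 is tied to 10 letters. Under the integer rule a loss of 11 to 14 letters gives 2 lines, so it meets the AE limit but falls outside the table's category above 2 lines.
- The 20/40 table is restricted to eyes 20/20 or better before surgery. The AE entry is not, and 20/25 eyes are eligible.
- SAP 6.5.8 equates an increase above 2.00 D with a change of −2 D or lower. Refraction is done in 0.25 D steps (Protocol Appendix B, 7.0), so exactly 2.00 D can occur. Such an eye is in the table but does not meet the AE limit.
- For entries 4, 12 and 14 the table shows the vision loss but not its combination with haze or interface epithelium.

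**4. Size.** Neither document gives a crossing rate or a reporting rate. As an illustration only, assume 8 true crossings of one type in 334 eyes:

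| Assumed share entered by sites | Eyes counted | Incidence (95% Clopper-Pearson) |
|---|---|---|
| 100% | 8 | 2.4% (1.0 to 4.7) |
| 75% | 6 | 1.8% (0.7 to 3.9) |
| 50% | 4 | 1.2% (0.3 to 3.0) |

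This shows how omissions pass through to the estimate. It is not evidence that they occur.

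**The case against.** The strongest reply has four parts.

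**The events are not lost.** A reader might infer that an unreported crossing is counted nowhere. The documents do not support that: for 8 of the 11 entries the underlying change appears in a SAP 6.5.8 table, and the IOP and slit-lamp values are listed by subject. This stands. The gap is confined to the AE incidence table, and is complete only for IOP, DLK and edema.

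**Checks are planned.** A reader might infer that nothing would reveal an omission. Protocol 3.3 has monitoring verify that adverse effects are reported. Protocol 10.1 has the medical monitor look at safety signals across sites. Protocol 10.3 has eCRFs verified against source, and 10.4 has out-of-norm values queried. Appendix A also ties a rigid-lens over-refraction to a BSCVA loss of 2 lines or more from Visit 1, so sites already make that comparison. This stands too, but none of it specifies a programmed comparison of AE entries with baseline or the previous visit. A BSCVA of 20/32 is an unremarkable value, yet it is a listed AE in an eye that was 20/20 before surgery.

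**The data-management documents are not visible.** The SAP sentence may describe only the table's row labels, and edit checks may exist elsewhere. That is possible. Read with Protocol 8.1 and the pairing with MedDRA terms, site entry is the natural reading; if edit checks exist, the SAP should cite them.

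**Derivation is neither clean nor complete.** Protocol Appendix B, 9.0 records edema on two scales plus a flap-edema code, and it grades DLK by stage, whereas the AE list says grade. Steroid-induced IOP rise is a separate complication. The rigid-lens result may not be a database field. The same open-label site also takes the measurements, so derivation catches omitted entries, not biased assessment. All of this limits the fix without removing the reason for it.

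**Conclusion.** The point holds in a limited form. The AE incidence table rests on site-entered categories, 11 of its 20 rows are measurement thresholds, and neither document derives those rows or specifies a programmed reconciliation. For 8 rows the underlying change is visible elsewhere under different definitions. For IOP, DLK grade 3 or above and corneal edema from 1 month on, there are only listings.

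The size of any undercount cannot be computed from the documents. A reader might also infer that the study's success is at risk. It is not: success depends on the three effectiveness endpoints (SAP 6.5.6.2.1.4), the safety summaries are descriptive, and no AE target value is stated. What is affected is the completeness of the AE incidence and which source is compared with the targets.

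The 8-of-11 match assumes that the SAP's logMAR conversion and integer-line rule apply to BSCVA in 6.5.8, and that the crossing occurs at a visit the by-visit tables cover.

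**What to change.** Amend SAP 6.5.8.2 and 6.5.8.3 as follows.

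1. Derive the measurement-defined AE rows in ADaM from recorded BSCVA, manifest refraction, IOP and slit-lamp findings, using the AE list's own letter, diopter and mmHg limits. First state which edema scale is used and that DLK stage maps to grade.
2. Before lock, list every eye where the derived and reported AEs disagree, and query it.
3. After queries are resolved, tabulate an eye as having the AE if it is derived or reported.
4. State that this is the source compared with the target values.
5. Keep investigator-reported categories for events that need judgement, including the rigid-lens condition if that result is not a database field.

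The cost is SAP wording, some derivation programming and one reconciliation listing. No new data are needed. AE incidence may rise slightly, for example from transient early BSCVA loss.
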